The proposed study is a phase 2, open-label study of tofakinib in treatment of patients with chronic pouchitis. Patients with chronic active pouchitis will be recruited from the Cedars-Sinai Inflammatory Bowel Disease Center. The total expected duration of participation is 16 weeks including a 4-week screening period, 8 weeks of tofakinib therapy and an end of study visit 4 weeks after completion of 8-week tofakinib treatment. Subjects experiencing early withdrawal from study will be scheduled for a safety follow-up visit 4 weeks after the date of withdrawal. The primary outcome is a reduction in the mPDAI score ≥ 2 at week 8 compared to baseline. We will also assess secondary outcomes including changes in clinical symptoms, fecal calprotectin, HRQOL, and mucosal appearance.

Figure 1: Study Design

Study Population

The study will be open to adult patients (ages 18-80 years) seen at the Cedars-Sinai Inflammatory Bowel Disease Center who meet eligibility criteria.

Inclusion criteria

1. Male or female subjects ages 18 to 80

2. Subjects with a history of proctocolectomy with ileal pouch anal anastomosis (IPAA) for UC at least 6 months prior to screening.
3. Subjects with pouchitis that is chronic, defined by a mPDAI score ≥ 5 assessed as the average from 3 days immediately prior to the baseline study visit and a minimum endoscopic subscore of 2 (outside the staple or suture line) with either (a) ≥ 3 recurrent episodes within 1 year prior to the screening treated with ≥ 2 weeks of antibiotic or other prescription therapy, (b) requiring maintenance antibiotic therapy taken continuously for ≥ 4 weeks immediately prior to the baseline study visit, or (c) not responding to $>= 4$ weeks of antibiotic therapy.
4. Women of childbearing potential must have documentation of a negative pregnancy test at screening and must agree to use two highly effective methods of birth control during the study and for at least 1 month after completion of study drug dosing.
5. Subjects willing and able to give informed consent.

Exclusion criteria

1. Subjects with IPAA surgery done for Crohn's disease (CD) or familial adenomatous polyposis (FAP) indications.
2. Subjects with CD-like complications including non-anastomotic strictures and active perianal fistulae, isolated or predominant cuffitis or mechanical complications of the ileal pouch.
3. Surgical complications such as anal stenosis, anastomotic leak, or fistula.
4. Subjects with prior exposure to tofacitinib.

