18. Subjects with condition(s) that in the opinion of the study investigators, may interfere with the participants ability to comply with the study procedures.

Concomitant medications

Study subjects will be allowed to remain on permitted concomitant medications provided the patient is on a stable dose for \geq 2 weeks prior to starting tofacitinib. Patient will need to stay on stable doses of these medications for the study duration of 8 weeks.

1. Antibiotics
2. Antidiarrheal agents
3. Oral corticosteroids including budesonide, up to doses of prednisone 20mg daily (or equivalent), or budesonide 9mg daily.
4. Probiotics

The following medications will not be allowed during the study:

1. Azathioprine, 6-mercaptopurine, or methotrexate within the 28 days prior to dosing visit.
2. Adalimumab, infliximab, golimumab, etanercept, certolizumab or vedolizumab within the 60 days prior to the first study visit or with negative drug concentration
3. Ustekinumab within 120 days prior to the first dosing visit or with negative drug concentration.
4. Intravenous corticosteroids within the 14 days prior to the first dosing visit.
5. Topical mesalamine or topical steroid within the 14 days prior to the first dosing visit.
6. Mycophenolic acid, tacrolimus, or cyclosporine within 60 days prior to the first dosing visit.

Treatment with Tofacitinib

Eligible subjects will be given tofacitinib 10mg twice daily for an 8-week duration. Study drug will be supplied for 4 weeks each at the baseline and week 4 visits.

Study Visits and Procedures

There are 5 study visits and 2 pouch endoscopic procedures during this 12-week study.

Screening Period (Week -4 to Day 0)

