At the week 4 and week 8 visit, the subjects will undergo assessment for concomitant medication use, adverse effects and compliance with the study drug. Physical assessment will include vital signs and a symptom driven targeted physical examination. Blood, urine and stool will be collected for hematology, chemistry, CRP, urinalysis and fecal calprotectin measurement. Symptom diary will be reviewed, and subjects will complete the CGQL questionnaire. At the end of week 4 visit, the second 4-week supply of the study drug will be dispensed to the subjects. At the end of 8 weeks, the subjects will stop taking the study drug and undergo a pouch endoscopy with biopsies for calculation of mPDAI score to assess treatment response. The pouch endoscopy will be scored by a central reader to reduce the risk of bias.

Week 12 (± 3 days) or Early Termination Visit

The week 12 visit will be the final visit. Subjects who are withdrawn earlier from the study (per study rules and subjects who withdraw consent) after receiving study medication will complete

an early termination visit. At this visit, subjects will undergo a physical assessment, review of medications, adverse event assessment and blood, urine and stool collection for hematology, chemistry, CRP, urinalysis and fecal calprotectin measurement. Symptom assessment and CGQL questionnaire completion will also be performed.

Table 1 - Schedule of Study Procedures and Visits

Study visit	Screening (Week -4 to day 0)	Baseline (Day 1)	Week 4	Week 8	Week 12
General					
Informed consent	x				
Medication/Medical History	x				
Smoking Status	x				
Height, weight, BMI	x	x	x	x	x
Vital Signs	x	x	x	x	x
12-lead ECG	x				
Physical Examination	x	x	x	x	x
Chest X-ray	x				
Tuberculosis and HBV testing	x				
Study Drug Dispensing		x	x		
Clinical, laboratory, endoscopic and safety assessments					
Pregnancy Test (females only)	x				
Urine pregnancy test		x	x		
Chemistry, Hematology, Urinalysis	x		x	x	x
Stool C. difficile test	x				
Fasting Lipid Panel	x		x	x	x
C-Reactive Protein	x		x	x	x
Pouch endoscopy and biopsies	x			x	
Fecal calprotectin	x		x	x	x
Symptom Assessments	x	x	x	x	x
Concomitant medications	x	x	x	x	x
mPDAI		x		x	
Adverse event assessment			x	x	x
CGQL		x	x	x	x

Evaluation and Outcomes

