The primary outcome of the study is clinical response at 8 weeks (defined below) as a measure of treatment efficacy. Other efficacy endpoints will include individual clinical, biochemical, and endoscopic assessments. Key secondary outcomes include assessment for safety and health-related quality of life.

Primary Endpoint

1. Proportion of subjects with clinical response defined as reduction in mPDAI score ≥ 2 from baseline at 8 weeks.

Secondary Endpoints

1. The proportion of subjects with clinical response, defined as an mPDAI score of ≥ 5 at 8 weeks with ≥ 2 -point decrease from the baseline score at 8 weeks.
2. The proportion of subjects with clinical remission at 8 weeks, defined as mPDAI score of < 5 with a ≥ 2 -point decrease from the baseline mPDAI score.
3. Change in mPDAI score at 8 weeks compared to baseline.
4. Change in mPDAI clinical sub-score at week 4 and week 8 compared to baseline.
5. Change in mPDAI endoscopic sub-score at week 8 compared to baseline.
6. Change in IBD-related quality of life as measured by Cleveland Global Quality of Life (CGQL) at week 4 and week 8 compared to baseline.
7. Safety, as determined by incidence of treatment-emergent adverse events. Adverse events of interest will include thromboembolic events and herpes zoster.

Efficacy Assessments

Efficacy measurement

The following will be used for definitions of clinical, biochemical, and endoscopic efficacy:

1. Clinical response defined as an mPDAI score of ≥ 5 at 8 weeks with a 2-point decrease from the baseline mPDAI score.
2. Clinical remission defined as mPDAI score < 5 after 8 weeks of treatment.
3. Change in mPDAI score from baseline to week 8.
4. Change in clinical and endoscopic mPDAI sub-scores from baseline to week 8.
5. Change in fecal calprotectin from baseline to week 8.
6. Change in serum C-reactive protein from baseline to week 8.

Symptom Diary

The subjects will be required to maintain a paper-based symptom diary to be completed daily starting after the initial screening visit. The symptoms recorded will include frequency of bowel movements, fecal urgency, abdominal pain/cramps, fever and blood in stools. The symptoms during the 3 days preceding the study visits will be used for the calculation of the mPDAI score for each study visits.

Pouch disease activity

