Study subject demographics (age, gender, race), baseline characteristics (height, weight, and BMI), IBD history, prior IBD-related medication use, concomitant medications and baseline laboratory tests will be reported using descriptive statistics. All subjects in the study who received at least one dose of the study drug will be included for analysis. Missing data or early termination will be handled by non-responder imputation. Remission and response rate will be assessed using descriptive statistics. Change in mPDAI, CGQL scores, serum CRP and fecal calprotectin compared to baseline will be assessed using Wilcoxon signed-rank test. Adverse events will also be reported using descriptive statistics. Data will be considered significant at the two-sided p value of <0.05 where applicable.

Publication Plan

After the completion of the study and analysis of the data, we will submit the results of this study to national gastroenterology meetings (ie. Digestive Disease Week or American College of Gastroenterology Annual Meeting) followed by manuscript submission for publication in a high impact peer-reviewed journal.

Anticipated Project Timeline

Based on the clinical volume at Cedars-Sinai Medical Center, we anticipate enrolling 12 subjects in this research study over a period of 28 months. Last patient study visit will be 12 weeks later. This will be followed by data analysis and writeup/submission of study abstract and manuscript.

Task	Month											
	1-2	3-4	5-6	7-10	11-14	15-18	19-22	23-26	27-30	31-34	35-36	37-39
Obtain IRB approval												
Enrollment												
Final study visit												
Data analysis												
Prepare / submit abstract												
Prepare / submit manuscript												

References

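### No scoring rule for a subject who starts or increases an antibiotic or corticosteroid before week 8: unless withdrawn, such a subject can by default count as a responder

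*Combined protocol and SAP*

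**What the plan says.** Under Statistical Methods, Data Analysis, the analysis set is everyone dosed: "All subjects in the study who received at least one dose of the study drug will be included for analysis". The next sentence gives the only imputation rule: "Missing data or early termination will be handled by non-responder imputation". Response and remission rates are then reported descriptively.

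Under Primary Endpoint, the outcome is "Proportion of subjects with clinical response defined as reduction in mPDAI score" of at least 2 points from baseline at week 8. Neither this definition nor those of response and remission under Secondary Endpoints and Efficacy measurement mention other treatment.

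Under Concomitant medications, antibiotics and oral corticosteroids are on the permitted list, with this requirement: "Patient will need to stay on stable doses of these medications for the study duration of 8 weeks". A second list is introduced by "The following medications will not be allowed during the study", although its entries are mostly written as intervals before dosing or before the first visit. Neither list says what happens in the analysis if the requirement is breached.

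Withdrawal appears in two places. Overview of Study Design has "Subjects experiencing early withdrawal from study will be scheduled for a safety follow-up visit 4 weeks after the date of withdrawal". The section on the week 12 or early termination visit covers "Subjects who are withdrawn earlier from the study (per study rules and subjects who withdraw consent". The available text does not set out the rules to which that phrase refers.

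At weeks 4 and 8, "the subjects will undergo assessment for concomitant medication use, adverse effects and compliance with the study drug".

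**The concern.** Subjects enter with active chronic pouchitis, and many have been treated repeatedly with antibiotics. Some may start or escalate an antibiotic or corticosteroid before week 8. The protocol's own background treats these drugs as active: it describes ileal release budesonide as effective in 58-75% of patients with chronic pouchitis, and it cites improvement of pouchitis after antibiotics.

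If such a subject stays in the study and has a week 8 mPDAI, neither imputation trigger is met. A fall of 2 points or more is then counted as response, whichever drug produced it. There is no control arm in which the same events would occur and offset the effect. Compared with non-responder scoring, observed scoring of these subjects can only raise the reported rates.

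The plan already takes a conservative line by treating missing data and early termination as failure. A change of background therapy is a similar event on which it is silent.

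**Working it through.** There is no sample-size or power figure to reproduce: Sample Size Estimation says that none was calculated, and the 12 subjects in Anticipated Project Timeline are a recruitment expectation. The check is first of the rules and then of what one subject is worth.

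**Applying the rules to one subject.** Take a subject who was dosed, increased a corticosteroid at week 5 (a hypothetical date), was not withdrawn, and has a complete week 8 mPDAI that is 2 or more points below baseline.

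1. In the analysis set? Yes, because the subject was dosed.
2. Missing data? No.
3. Early termination? No, unless the unstated withdrawal rules apply. If they do, the subject is already a non-responder and there is no gap.
4. Endpoint met? Yes. The definition asks only for the fall in score.
5. Stable-dose requirement met? No, but nothing links that breach to scoring.

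The subject therefore counts as a responder by default. The same steps apply to remission.

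**Worth of one subject.** With n = 12, 1/12 = 8.3 percentage points. This is the difference between observed and non-responder scoring. It is an upper limit on the bias from that subject, who might have responded on tofacitinib alone.

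**Illustration**, assuming 6 observed responders (exact Clopper-Pearson 95% intervals):

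| Responders reclassified | Rate | 95% CI |
|---|---|---|
| 0 | 6/12 = 50.0% | 21.1 to 78.9% |
| 1 | 5/12 = 41.7% | 15.2 to 72.3% |
| 2 | 4/12 = 33.3% | 9.9 to 65.1% |

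**How often.** The documents give no frequency. If each subject had probability q of starting or increasing one of these drugs (assumed, and independent between subjects), the chance of at least one such subject among 12 is 1 - (1 - q)^12: 46% for q = 5%, 72% for 10%, 93% for 20% and 99% for 30%. This is the chance of a change occurring, not of a changed subject being counted as a responder, which is lower.

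**The case against.** The strongest reply is that the plan partly covers this. Subjects may only continue permitted drugs at a stable dose, so a start or increase breaches the protocol. If the withdrawal rules remove such a subject, the early-termination rule already makes the subject a non-responder. Concomitant medication is assessed, so with 12 subjects any change could be seen and described. The study is a single-arm, open-label pilot with no success threshold. Stable antibiotics and corticosteroids already limit attribution, and a shift of one or two subjects lies well inside the exact interval.

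Much of this stands. It limits the weight of the point but does not close the gap, because a conduct requirement is not a scoring rule and the withdrawal rules cannot be read. A wide interval also describes sampling error only; it does not allow for a shift in one direction.

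Three stronger readings are tempting, and the documents do not support them:

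- A reader might infer that the plan directs observed scoring of these subjects, or allows the changes. It does neither. Observed scoring is only what follows when nothing else is stated.
- A reader might combine the 58-75% budesonide figure with a guessed frequency of changes to predict the bias. That figure is not tied to a 2-point mPDAI fall or to 8 weeks, no corresponding rate is given for antibiotics, and some subjects enter because antibiotics failed.
- A reader might want every antibiotic course scored as failure. Safety Assessment names infections among the known potential adverse events of tofacitinib, so that rule could push the efficacy rate down for reasons unrelated to pouchitis.

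**Conclusion.** The point holds as a gap in scoring. For a dosed subject who starts or increases an antibiotic or corticosteroid before week 8, is not withdrawn, and has a week 8 score, the plan states no rule, and its default allows that subject to count as a responder or remitter. The possible bias in the response and remission rates is upward, by at most 8.3 points per affected responder at 12 subjects.

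This rests on two assumptions: that the unstated withdrawal rules do not already remove such subjects, and that about 12 are enrolled. The number of affected subjects is unknown and may be zero. What is at stake is the reading of a descriptive rate, not a formal decision. The label is cheap improvement.

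**What to change.** Add to Data Analysis:

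> For response and remission, subjects who, between first dose and the week 8 assessment, start or increase a corticosteroid, start or increase an antibiotic other than for a documented non-pouchitis infection, or start a drug named in the not-allowed list under Concomitant medications, are counted as non-responders and non-remitters.

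Then:

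- Report two sensitivity analyses: one on observed scores regardless of medication change, and one counting any antibiotic start or increase as non-response.
- List the affected subjects individually with drug, date and indication.
- Keep all dosed subjects in the Wilcoxon analyses, and state that those results include scores observed after medication changes.
- Reconcile the scoring rule with the stable-dose requirement and with the rules for withdrawal mentioned under the early termination visit, saying whether those rules cover such changes.

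This is a scoring rule only and does not change what care a subject may receive.

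**Cost.** One sentence, two short analyses and a listing. Concomitant medication is already assessed at weeks 4 and 8, but the text does not say that date, dose and indication are recorded, so case-report fields may be needed. The indication of each antibiotic course has to be classified, ideally before the week 8 score is known. The reported rate may be slightly lower.

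### Does the signed-rank test of week-8 mPDAI change need a stated value for dosed subjects who have no week-8 endoscopy?

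*Combined protocol and SAP*

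**What the plan says.** In Statistical Methods, Data Analysis, the analysis set is every treated subject: "All subjects in the study who received at least one dose of the study drug will be included for analysis". One sentence covers incomplete data: "Missing data or early termination will be handled by non-responder imputation". The binary outcomes are not tested: "Remission and response rate will be assessed using descriptive statistics". The continuous outcomes are: "Change in mPDAI, CGQL scores, serum CRP and fecal calprotectin compared to baseline will be assessed using Wilcoxon signed-rank test", at a two-sided 0.05 level.

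Under Pouch disease activity, the mPDAI is the sum of a 6-point clinical and a 6-point endoscopic score, so a total needs an endoscopy. Study Visits and Procedures says "There are 5 study visits and 2 pouch endoscopic procedures during this 12-week study". Table 1 puts the endoscopies at screening and week 8. At the end of treatment "the subjects will stop taking the study drug and undergo a pouch endoscopy with biopsies for calculation of mPDAI score". At the week 12 or early termination visit "subjects will undergo a physical assessment, review of medications, adverse event assessment and blood, urine and stool collection for hematology"; the rest of that paragraph adds symptoms and the CGQL, but no endoscopy.

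The primary endpoint is the proportion with a fall of at least 2 mPDAI points at week 8. Change in total mPDAI and change in the endoscopic sub-score are secondary endpoints 3 and 5. No sample size was calculated. The Anticipated Project Timeline says "we anticipate enrolling 12 subjects in this research study over a period of 28 months".

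**The concern.** Non-responder imputation assigns a category, whereas a signed-rank test needs a paired difference. A treated subject who leaves before week 8 stays in the analysis set and counts as a non-responder, but has no total mPDAI to subtract from baseline. The statement under Pouch disease activity that the score is calculated at every visit does not help, since no other on-treatment endoscopy is scheduled.

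Response and remission are only described, so the plan's efficacy p-values come from the change tests. If the software silently drops incomplete pairs, a test on those with a week-8 endoscopy would stand beside a response rate over all treated subjects. If subjects left because the drug was not working, the change result would look too favourable. With 12 subjects in an open-label study, a value chosen after seeing the data would be an avoidable freedom.

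**Working it through.** The plan has no power or sample-size figure to reproduce, so the check asks how far the result depends on the unstated value. All mPDAI changes and all dropout below are assumed.

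**Inputs from the documents.** 12 subjects (Anticipated Project Timeline); two-sided 0.05 and the signed-rank test (Data Analysis); response is a change of -2 or lower (Primary Endpoint); baseline mPDAI is at least 5 (Inclusion criteria) and the maximum is 6 + 6 = 12 (Pouch disease activity). A non-responder's change can therefore lie anywhere above -2, up to 12 - 5 = +7.

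**Method.** Rank the absolute changes with mid-ranks for ties and let W+ be the rank sum of the positive changes. The exact two-sided p is the share of the 2^m sign patterns (m non-zero changes) whose W+ is at least as far from half the rank total as the observed W+. Zeros are either dropped (the usual test) or ranked first and then set aside (Pratt).

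**Example 1: 10 observed, 2 missing.** Observed changes -4, -3, -3, -2, -2, -2, -1, -1, +1, +2.

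| Handling of the 2 missing subjects | W+ / rank total | p |
|---|---|---|
| Omitted | 7.5 / 55 | 48/1024 = 0.047 |
| Zero change, zeros dropped | 7.5 / 55 | 48/1024 = 0.047 |
| Zero change, Pratt | 11.5 / 75 | 50/1024 = 0.049 |
| -1 each | 10.5 / 78 | 104/4096 = 0.025 |
| +1 each | 16.5 / 78 | 360/4096 = 0.088 |
| +2 each | 21.5 / 78 | 778/4096 = 0.190 |
| +7 each | 30.5 / 78 | 2148/4096 = 0.524 |

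The first three rows are the natural readings, and they agree within 0.002. The others show that the word non-responder alone does not fix p.

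**Example 2: 9 observed, 3 missing, built to be borderline.** Observed changes -5, -4, -4, -3, -3, -2, -1, +1, +2.
- Observed cases: W+ = 1.5 + 3.5 = 5 of 45; p = 20/512 = 0.039; median -3.0.
- Zero change, zeros dropped: the same p, 0.039.
- Zero change, Pratt: W+ = 4.5 + 6.5 = 11 of 72; p = 28/512 = 0.055; median of 12 = (-2 + -1)/2 = -1.5.
- Response rate under the existing rule: 6/12 in every case.
- If all 9 observed subjects improve, p = 2/512 = 0.004 under either reading.

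**Simulation.** Rounded normal changes with (mean, SD) of (-1.8, 2.3), (-2.5, 2.0) and (-1.2, 2.0); 20,000 trials per setting; stopping independent of outcome. Observed cases with zeros dropped are compared with zero change under Pratt.

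| Early stops of 12 | Mean shift of median toward zero | Trials losing significance | Trials gaining it |
|---|---|---|---|
| 0 | none | 0.5-1.9% | 0.3-2.0% |
| 1 | 0.20-0.25 | 0.8-2.5% | 0.8-2.5% |
| 2 | 0.43-0.53 | 1.3-2.8% | 1.0-2.7% |
| 3 | 0.65-0.86 | 1.4-2.0% | 1.4-2.5% |

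With early stops, losses and gains nearly cancel: the largest net difference is 2.5 - 2.0 = 0.5 percentage points. The zero-stop row shows that much of the flipping comes from switching to Pratt. The median shift is the distance between two conventions and not an estimate of bias, because stopping was made independent of outcome and the plan never names the median as its summary.

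**The case for a change.** The strongest argument for acting is that the plan contains the test and the imputation rule but no link between them, and that a few sentences written before analysis would supply it. Values compatible with non-response can take p from 0.025 to 0.524 in the first example. Even if zero change is taken as understood, the treatment of zeros stays open, and the usual test then returns exactly the observed-case p.

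That the text is silent stands. The step from silence to a required change does not. The wide range of p comes from assigning worsening to every leaver, which the plan does not suggest. Any specific rule would be a preference: observed cases, zero change, baseline carried forward and worst rank are all in use, and each has a cost. Zero change understates benefit in someone who improved and left for an unrelated reason, and understates harm in someone who left because of worsening.

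A fuller prescription also brings problems of its own. Requiring Pratt alters the test when nothing is missing. Leaving the CGQL, clinical sub-score, CRP and calprotectin as observed-case tests keeps the mismatch of denominators. Barring early-termination values would discard useful data in one ordinary case: the Overview of Study Design sets the follow-up 4 weeks after withdrawal, so a subject leaving at week 4 is seen at week 8.

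**Conclusion.** No change to the plan follows. This is missing detail on a secondary analysis that analysts fill sensibly, combined with a trade-off on which reasonable statisticians differ. The primary endpoint and the remission rate are fully determined by the existing rule. For the change in total mPDAI, and in the endoscopic sub-score if it is tested, the choice between the two natural readings moves the proportion of significant trials by at most about 0.5 percentage points. It affects individual results only near the threshold. What can visibly differ is the summary of change and its n, which a report showing the number analysed for each test makes plain.

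This rests on 12 treated subjects, 1 to 3 assumed early stops (8% to 25%), the assumed distributions of change, and stopping independent of outcome. Outcome-related stopping would make an observed-case summary too favourable by an amount the documents give no means of estimating. The response rate over all treated subjects, reported beside it, already counts those subjects as failures.
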